15.2.2. MISSING DATA METHODS FOR SECONDARY EFFICACY VARIABLE(S)

E-diary entries will be used to estimate missing stool frequency and rectal bleeding scores as these values are recorded daily in the e-diary. Endoscopy sub score missing data methods are also specified in section 7.3

Document: \\iedc-vnasc01\BIOSdata\Abivax\ABX464\FZA92720\Biostatistics\Documentation\SAP\ABX464-103_SAP_V2.0_10MAY2021

Author: [REDACTED] Version Number: 2.0
Version Date: 10May2021

Template No.: CS_TP_BS016 Revision 5

Reference: CS_WI_BS005

Effective Date: 01Apr2018

15.2.3. ANALYSIS OF SECONDARY EFFICACY VARIABLES

15.2.3.1. Analysis of Secondary Variables at Week 8 and at Week 16

In addition to the descriptive statistics as described in Section 15.2 and specific subsections of Section 15.2. ANCOVA models, using the same procedure as described for the primary efficacy analysis in section 15.1.3, will be used to make the assessments listed below:

- Global effect of ABX464 treatment vs placebo in change from baseline in MMS at Week 8
- Combined number and percentage of patients in clinical remission at Week 8 and Week 16
- The number and percentage of patients with clinical response at Week 8 and Week 16
- The number and percentage of patients with endoscopic improvement and remission, by segment at Week 8 and Week 16
- Proportion of patients with mucosal healing at Week 8 and Week 16
- Daily stool frequency and number of patients with reduction relative to baseline in stool frequency sub-score at every study visit
- Number of patients with reduction relative to baseline in rectal bleeding sub-score at each visit
- Frequencies and percentages for rectal bleeding and stool frequency sub-score categories
- Frequencies and percentages for Mucosal Appearance at endoscopy by segment
- Total IBDQ scores and change from baseline at Week 8 and Week 16

In addition, the above variables will be included in a listing by patient. The frequency of daily stools and categories of rectal bleeding as recorded in the e-Diary will be listed for the duration of the study.

[REDACTED]

[REDACTED]

[REDACTED]

Document: \\ieddc-vnasc01\BIOSdata\Abivax\ABX464\FZA92720\Biostatistics\Documentation\SAP\ABX464-103_SAP_V2.0_10MAY2021

Author: [REDACTED]

Version Number: 2.0
Version Date: 10May2021

Template No.: CS_TP_BS016 Revision 5

Reference: CS_WI_BS005

Effective Date: 01Apr2018

15.2.3.2. Analysis of Number and Percentage of Patients in Clinical Remission at Week 8

The proportion of patients with clinical remission at Week 8 will be compared across study treatment arms using a stratified Mantel-Haenszel test to estimate the common odds ratio for each active arm vs placebo, with exposure to previous biological or JAK inhibitors as the stratification factor. As the common odds ratio is calculated under the assumption that the underlying odds ratio is homogeneous across the strata, the hypothesis of homogeneity of the odds ratio across strata will be tested using the Breslow-Day test. The chi-square, degrees of freedom and corresponding p-value for the Breslow-Day test for homogeneity of the odds ratios will be presented. A p-value less than 5% will indicate that the assumption of a common odds ratio is unreasonable. In this case, the Cochran-Mantel-Haenszel estimate of the common odds ratio will not be reported, but rather the strata-specific (i.e. previous exposure to biological or JAK inhibitors) estimates of the odds ratio.

If a sample size is too small for the hypothesis of homogeneity of the odds ratio to be tested by the Breslow-Day test, the stratum -specific or unstratified odds ratio will be determined.

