9.2. Efficacy Analysis

Analysis of efficacy data will be carried out in the Full Analysis Set in which subjects who prematurely discontinue the study due to adverse reaction(s) will be considered treatment failures.

The primary efficacy endpoint of the study is the change in the Modified Mayo Score (MMS) from Baseline to Week 8. This change will be compared between subjects who received ABX464 and placebo for each ABX464 treatment arm separately using an ANCOVA model adjusting for randomized study treatment arm, previous biological or JAK inhibitors treatment use (i.e. randomization strata), and baseline MMS.

The dose testing will commence with comparing the ABX464 50mg dose with placebo. If this is significant at a 5% two-sided level (i.e. $p < 0.05$) a comparison against placebo will be carried out at the ABX464 100mg dose. Again, if significance at a 5% level for this test is observed the procedure will be repeated at the ABX464 25mg dose. In this closed procedure no adjustment for multiple comparison is needed. Should the data warrant it, testing between doses may also be conducted.

In addition, descriptive statistics will be presented by treatment arm for all secondary efficacy variables for each measurement timepoint.

These statistics include:

- Continuous variables: mean, standard deviation, minimum and maximum, 95%
- Confidence intervals for the mean, median and quartiles will be presented.
- Categorical variables: counts, rates and 95% confidence intervals for the rates will be calculated.

In addition to descriptive statistics, the following analyses will also be carried out for the variables indicated below:

- The global (combined) ABX464 treatment effect vs. placebo in the change from Baseline in Modified Mayo Score at Week 8
- The proportion of subjects with clinical remission at Week 8 will be compared across study treatment arms using a stratified Mantel-Haenszel test.
- Mixed model analysis of covariance will be conducted for the following measurements:
 - The change from baseline in microRNA-124 levels in total blood (PAXgene®) at Week 1, Week 4, Week 8 and Week 16 and in tissue (RNA later).
 - The change from baseline in fecal calprotectin levels at Week 8 and Week 16.
 - The change from screening in the histopathology/infiltrate (rectal/sigmoidal biopsies) assessed by the Robarts Histopathology Index, the Geboes and Nancy Histology Scoring Scales at Week 8 and Week 16 (if available).

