15.1.3. PRIMARY ANALYSIS OF PRIMARY EFFICACY VARIABLE

The primary efficacy analysis will be performed for FAS and PPAS.

The primary objective of this study is to determine an optimal ABX464 dose to be used in moderate to severe active ulcerative colitis patients who have failed or are intolerant to immunomodulators, Anti-TNF α , vedolizumab, JAK inhibitors and/or corticosteroids by comparing the mean change from baseline in the MMS at Week 8 for the three ABX464 dose levels to the placebo. An analysis of covariance (ANCOVA) model will be used to assess these changes.

The ANCOVA model for Change from Baseline MMS at Week 8 will include the fixed treatment effect, the previous use of biological or JAK inhibitors effect and the covariate, baseline MMS and a random error term.

The assumptions that the random errors in the ANCOVA model are normally distributed with homogeneity of variances will be checked. If either the hypothesis regarding normality of errors or the hypothesis of equal variances is rejected at the 5% significance level a nonparametric ANCOVA using the ranked data will be performed to test for differences in the mean change from baseline. The least square means and confidence intervals from the parametric ANCOVA will also be presented.

The dose testing will commence with comparing the ABX464 50mg dose with placebo. If this is significant at a 5% two-sided level (i.e. $p < 0.05$) a comparison against placebo will be carried out at the ABX464 100mg dose. Again, if significance at a 5% level for this test is observed the procedure will be repeated at the ABX464 25mg dose. If in this sequence of comparisons of ABX464 dose levels to placebo one is not significant (i.e., $p \geq 0.05$) the additional comparisons to placebo will not be

Document: \\iedc-vnasc01\BIOSdata\Abivax\ABX464\FZA92720\Biostatistics\Documentation\SAP\ABX464-103_SAP_V2.0_10MAY2021

Author: [REDACTED]

Version Number:
Version Date:

2.0
10May2021

Template No.: CS_TP_BS016 Revision 5

Reference: CS_WI_BS005

Effective Date: 01Apr2018

performed. Should any of these comparisons with the placebo treatment group be significant, further exploratory testing of the dose groups against each other will be conducted at the same significance level. A global comparison of all active treatment groups vs placebo group will also be conducted.

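### SAP 15.2.3.1 sends yes/no secondary endpoints to the primary ANCOVA; read as one four-arm model, its single error variance misstates standard errors whenever response rates differ between arms

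*SAP*

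**What the plan says.** SAP 15.2.3.1 states that "ANCOVA models, using the same procedure as described for the primary efficacy analysis in section 15.1.3, will be used to make the assessments listed". Among the listed items are clinical response, endoscopic improvement and remission by segment, "Proportion of patients with mucosal healing at Week 8 and Week 16", combined Week 8 and Week 16 remission, numbers of patients with a reduction in the stool frequency or rectal bleeding sub-score, and "Frequencies and percentages for rectal bleeding and stool frequency sub-score categories". IBDQ and the global MMS effect, which suit ANCOVA, are on the same list.

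SAP 15.1.3 defines that procedure: fixed effects for treatment and prior biologic/JAK use, baseline MMS as covariate, and one random error term. SAP 7.1 gives treatment four levels. If normality or equal variance is rejected at 5%, "a nonparametric ANCOVA using the ranked data will be performed to test for differences in the mean change from baseline", and the parametric least-squares means and intervals are still presented. If any dose beats placebo, "further exploratory testing of the dose groups against each other will be conducted at the same significance level".

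Only Week 8 clinical remission has a binary method. SAP 15.2.3.2 uses a stratified Mantel-Haenszel test "to estimate the common odds ratio for each active arm vs placebo".

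Protocol 9.2 plans no ANCOVA for proportions. It says "Categorical variables: counts, rates and 95% confidence intervals for the rates will be calculated", and adds one test: "The proportion of subjects with clinical remission at Week 8 will be compared across study treatment arms using a stratified Mantel-Haenszel test". SAP 3.3 does not list the ANCOVA as a change from the protocol.

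**The concern.** A yes/no outcome with rate p has variance p(1−p), so arms with different rates have different variances. A joint four-arm ANCOVA replaces these with one average and uses it for every contrast. The intervals and tests are then wrong by an amount, and in a direction, set by the pattern of rates across arms. Low-rate endpoints such as endoscopic remission and mucosal healing are the most exposed.

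The trial's stated aim is to find an optimal dose, so readers will compare doses on endoscopy and healing. A frequency table is not an ANCOVA response at all, so that part of the list cannot be carried out as written. Week 8 remission is handled by one method and similar endpoints by another, with no reason given.

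**Working it through.** **What the plan states.** It gives no rate, standard error or power for the yes/no endpoints. Its only design figure is the primary sample size, which reproduces: with a difference of 1.5 and SD 2.1, a t-test with 55 evaluable per arm has 96.0% power, and 55/0.95 = 57.9, rounded up to 58. That was later raised to 61.

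**Inputs.**
- 61 per arm (Protocol 9.4).
- Phase IIa rates from Protocol 1.3: endoscopic improvement 11.1% placebo and 50% active; clinical response 33% and 70%. They come from 32 patients at the 50 mg dose only; rates for the other doses are assumed.
- Mucosal healing: the documents give no rate. 5% and 20% are assumed.

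**Formulas.** With v = p(1−p) and equal arms, the joint model uses MSE = mean of the four v. Then SE ratio = √[2·MSE/(v₁+v₂)] for the two arms compared. Approximate false-positive rate = 2[1−Φ(1.96 × ratio)], and approximate coverage is one minus that quantity.

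**Worked case.** At 11.1% and 50% in all doses, v is 0.0987 and 0.25, and MSE = (0.0987 + 3 × 0.25)/4 = 0.2122.
- Against placebo: pooled SE √(0.2122 × 2/61) = 0.0834; correct SE √[(0.0987 + 0.25)/61] = 0.0756; ratio 1.103.
- Dose versus dose: √(0.2122/0.25) = 0.921.

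| Pattern | Comparison | SE ratio | Approximate consequence |
|---|---|---|---|
| 11.1%; all doses 50% | dose vs placebo | 1.103 | coverage 96.9% |
| same | dose vs dose | 0.921 | false positives 7.1% |
| 11.1%; one dose 11.1%, two at 50% | inactive dose vs placebo | 1.329 | type I error 0.9% |
| same | working dose vs placebo | 1.000 | none |
| same | two working doses | 0.835 | false positives 10.2% |
| 11.1%; only one dose at 50% | working dose vs placebo | 0.885 | coverage 91.7% |
| same | two inactive doses | 1.176 | false positives 2.1% |
| 33%; all doses 70% | dose vs placebo | 0.994 | negligible |
| Assumed 5%; all doses 20% | dose vs placebo | 1.127 | coverage 97.3% |

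**Simulation.** The SAP 15.1.3 model was fitted to 0/1 outcomes, under several assumed covariate effects including none, and compared with Mantel-Haenszel stratified by prior exposure (about 50% assumed in most runs).
- 11.1%/50% in all doses: coverage about 97%; dose-versus-dose false positives 6.4–7.4% (Mantel-Haenszel 4.8–6.0%).
- One inactive dose: 9.9–10.2% between the two working doses (Mantel-Haenszel 5.0–5.6%). Type I error of the inactive dose against placebo is 0.7–1.0% (Mantel-Haenszel 4.8–5.0%).
- Only one working dose: coverage against placebo 91.8–92.0%; the two inactive doses differ falsely in 1.8–2.0%.
- Assumed 5%/20%: power against placebo 62–65%, against 72–75% for Mantel-Haenszel.
- If all arms share 11.1%, type I error is 4.7%, so there is no distortion.

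**Why the fallback does not help.** Among N patients with n₀ zeros, mid-ranks of a 0/1 outcome are (n₀+1)/2 for a zero and (n₀+1)/2 + N/2 for a one. That is a linear rescaling, so the t statistics are identical. Ranking baseline MMS as well left the dose-versus-dose decision unchanged in 99.7–99.9% of comparisons. The normality check rejected in every one of 2,000 simulated trials per setting, so the fallback would in effect always be used.

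**Denominators.** SAP 15.2.1.4 and 15.2.1.5 divide by patients in the arm at Week 8 without defining that group. With 61 randomized, 5% missing and half of observed patients improving, the overall endoscopic improvement rate is 29/58 = 50.0% among those observed, or 29/61 = 47.5% with missing as failure. With the SAP 7.3 placebo-neighbour value it is 0.95 × 50 + 0.05 × 11.1 = 48.1%.

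**The case against.** The strongest reply is that a linear model for 0/1 data is not itself the fault. This is right. Every distortion above comes from pooling variance over four arms. Separate two-arm ANCOVAs on the same data largely remove it: at 11.1%/50%, coverage is 94.7% and dose-versus-dose false positives 4.7%; with one inactive dose, its type I error is 5.5%. Protocol 9.2 speaks of comparing each arm separately, and neither document says outright that one joint model is fitted. The four-level factor in SAP 7.1 makes the joint model the better reading, but the finding depends on it. Two-arm fits are not a complete answer for rare events: at an assumed 2% and 10%, their coverage was 92.6%.

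A reader might infer that ANCOVA always makes comparisons with placebo conservative when the placebo rate is low. It does not: with one working dose the interval is too narrow.

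The stakes are limited. Protocol 9.2 calls p-values descriptive, and SAP 15.1.3 calls dose-versus-dose testing exploratory. Applying that testing to these endpoints follows only from the reference to the same procedure. Three redacted lines end SAP 15.2.3.1 and may add a method, although the visible sentence assigns ANCOVA plainly.

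A reader might also take the Week 8 denominators as a contradiction with the non-responder rule. SAP 2.3 and 7.3 confine that rule to remission and response, SAP 7 allows denominators based on available data, and SAP 15.2.2 points endoscopy to SAP 7.3. This is an ambiguity.

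**Conclusion.** The concern stands. Under the joint-model reading, SAP 15.2.3.1 produces wrong intervals and tests for yes/no endpoints whose rates differ between arms. With two or three working doses and a low placebo rate, some or all comparisons with placebo are too conservative, and tests between working doses reject falsely at about 7–10%. With one working dose, its interval against placebo covers about 92%, and the test between the inactive doses is too conservative, at about 2%. At rates like Phase IIa clinical response the error is negligible.

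These sizes rest on Phase IIa rates from a small trial, assumed patterns across doses, equal arms, and an assumed mucosal healing rate. Unequal arms from the US allocation, which omits 100 mg, were not modelled because US numbers are not given.

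It would be a mistake to infer that the primary conclusion is at risk. The primary endpoint is the change in MMS, a score from 0 to 9, and this argument does not touch its analysis. Week 8 clinical remission is also unaffected, having its own test.

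**What to change.** - For every yes/no endpoint in SAP 15.2.3.1, replace the pooled ANCOVA with the stratified Mantel-Haenszel method of 15.2.3.2. Logistic regression, or a linear model with arm-specific variances, adjusted for prior biologic/JAK exposure and baseline MMS, is equally acceptable.
- State that the method also serves dose versus dose if those tests are kept; 15.2.3.2 now covers only each active arm against placebo.
- Name an exact method for sparse or empty cells in any arm or stratum. At 58 per arm, some arm-by-stratum cell had no events in 41% of simulated trials at an assumed 5%/20%, and in 82% at 2%/10%. The chance of no placebo events at all is 0.95⁶¹ to 0.95⁵⁸ = 4–5% at a 5% rate, and 29–31% at 2%.
- Present category frequencies descriptively, keep ANCOVA for MMS and IBDQ, and record the change in SAP 3.3.
- First define the Week 16 and combined Week 8/16 endpoints so that they handle Week 8 endoscopic improvers, who have no Day 113 endoscopy by design (Protocol 3.1.1). At the Phase IIa rates that is about 0.50 × 61 ≈ 30 patients in an active arm and 0.111 × 61 ≈ 7 on placebo.
- Drafting: state one Week 8 denominator for overall endoscopy and mucosal healing, for example all FAS patients with missing as non-responder, and say that it replaces the 7.3 endoscopy imputation there. Do not count an unscored segment as a failure in by-segment tables. The clinical response formula in 15.2.1.3 has remission in its numerator and should say response.

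The cost is SAP wording and re-use of existing code. Mantel-Haenszel gives up the baseline-MMS adjustment; at 33% and 70% with 58 per arm, simulated power moves from 98.9% to 98.6%. Reported rates may fall slightly, for example from 50% to 47.5% at 5% dropout.

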5.3.5. IBD Questionnaire (IBDQ)

The Inflammatory Bowel Disease Questionnaire (IBDQ) is a widely used questionnaire for HRQoL assessment in patients with inflammatory bowel diseases (IBDs). This questionnaire has been adapted

and validated into several languages. IBDQ will be filled in by the patients at Day 1, Day 57 and Day 113 prior to any study procedures.

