 - The change from screening in Modified Mayo scores and Partial Mayo scores during the study.

In this mixed model, treatments and stratum will be fixed effects, subject will be random effect and baseline values of the respective measurements will be covariates. Other explanatory variables will also be allowed to be included in the model. To normalize eventual skewed distributions transformation of the data will also be considered. Study treatment groups will be compared within this model framework. All p-values will be interpreted in a descriptive manner.

The following subgroups will be analyzed:

- Gender
- Age
- Country
- US vs non-US
- Baseline MMS
- With/without previous biological or JAK inhibitors treatment
- Week 16 ABX464-NGlu AUC0-12 level above/below 7 000 h*ng/mL (vs. placebo)
- Concomitant UC medications.

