7.1. ADJUSTMENTS FOR COVARIATES AND FACTORS TO BE INCLUDED IN ANALYSES

The following covariates and factors will be used in the analyses. For details of their inclusion in the models, see the specific analysis section.

Covariates

- Baseline MMS
- Baseline pMMS
- Baseline Fecal Calprotectin level
- Baseline Geboes Score
- Baseline Nancy Score
- Baseline RHI

Factors

- Treatment arm (ABX464 100mg, ABX464 50 mg, ABX464 25mg, Placebo)

Document: \\iedc-vnasc01\BIOSdata\Abivax\ABX464\FZA92720\Biostatistics\Documentation\SAP\ABX464-103_SAP_V2.0_10MAY2021

Author: [REDACTED]

Version Number:

2.0

Version Date:

10May2021

Template No.: CS_TP_BS016 Revision 5

Reference: CS_WI_BS005

Effective Date: 01Apr2018

- Previous biologic or JAK inhibitors treatment use (Yes/No)

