15.2.3.3. Analysis of Secondary Variables Measured Repeatedly Over Time

In addition to descriptive statistics as described in Section 15.2, mixed model repeated measures ANCOVA will be used to assess the following secondary variables:

- Change from screening in MMS to Week 8 and Week 16 and change from baseline to all post-baseline visits in pMMS during the study, by treatment group vs placebo group.
- The change from baseline in fecal calprotectin levels at Week 8 and Week 16.
- The change from screening in the histopathology/infiltrate (rectal biopsies) assessed by the Robarts Histopathology Index, the Geboes and Nancy Histology Scoring Scales at Week 8 and Week 16 (if available).

Mixed Model for Repeated Measures (MMRM) will be used to analyze change from baseline in MMS, pMMS, fecal calprotectin, RHI, Geboes and Nancy scores. Change from baseline at the specified Week

Document: \\ieedc-vnasc01\BIOSdata\Abivax\ABX464\FZA92720\Biostatistics\Documentation\SAP\ABX464-103_SAP_V2.0_10MAY2021

Author: [REDACTED]

Version Number: 2.0
Version Date: 10May2021

Template No.: CS_TP_BS016 Revision 5

Reference: CS_WI_BS005

Effective Date: 01Apr2018

will be analyzed by using a MMRM model with baseline value as a covariate, fixed effects for treatment group, exposure to previous biologics or JAK inhibitors, visit, visit by treatment group interaction and a random error term. For the MMRM model, the Kenward-Roger method for approximating the denominator degrees of freedom and correcting for bias in the estimated variance-covariance of the fixed effects will be used. This will be achieved by specifying the DDFM = KR option in the MODEL statement within PROC MIXED. An unstructured covariance will be selected initially, and if convergence is not achieved with this structure, the following covariance structures will be used in the order listed until convergence is achieved: Toeplitz (TOEP), Autoregressive (AR) and Compound Symmetry (CS).

The strata US vs non-US sites will not be included as a factor in the model as the stratification occurs only because US patients will not receive 100 mg dose of ABX464.

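### IBDQ and daily stool frequency are modelled with baseline MMS but not their own baselines, which costs precision and lets the IBDQ score and change models disagree

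*SAP*

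**What the plan says.** SAP 15.2.3.1 states that "ANCOVA models, using the same procedure as described for the primary efficacy analysis in section 15.1.3, will be used" for a list of secondary variables. Two of the entries are "Total IBDQ scores and change from baseline at Week 8 and Week 16" and "Daily stool frequency and number of patients with reduction relative to baseline in stool frequency sub-score at every study visit".

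The model in SAP 15.1.3 contains treatment, then "the previous use of biological or JAK inhibitors effect and the covariate, baseline MMS and a random error term". SAP 15.1.1 takes the screening MMS as baseline, because MMS is not calculated on Day 1.

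SAP 7.1 opens with "The following covariates and factors will be used in the analyses". It names as covariates the baselines of MMS, pMMS, fecal calprotectin, Geboes, Nancy and RHI, and as factors the treatment arm and previous biologic or JAK inhibitor use. These six covariates match the six outcomes of SAP 15.2.3.3, where change from baseline "will be analyzed by using a MMRM model with baseline value as a covariate". Baseline IBDQ and baseline stool frequency do not appear in SAP 7.1.

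Both baselines are available. Protocol 5.3.5 states that "IBDQ will be filled in by the patients at Day 1, Day 57 and Day 113", and Protocol 5.2.1 has the e-diary kept daily from screening.

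**The concern.** For a continuous outcome, its own baseline is usually the strongest predictor of follow-up. A change score analysed without that baseline has a larger error variance than necessary. It also carries any chance baseline imbalance between arms into that trial's contrast. Baseline MMS is an indirect stand-in for IBDQ: it is a different instrument, taken at screening rather than on Day 1.

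At stake are the quality-of-life and stool-frequency comparisons with placebo. There is also a reporting problem. The SAP models both the IBDQ score and the IBDQ change. Without baseline IBDQ in the model, the two can give different treatment effects from the same patients, and no rule says which one counts.

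**Working it through.** **The plan's own figure.** The documents give no power or precision figure for IBDQ or stool frequency. The only sample-size figure is for MMS (Protocol 9.4): 58 × 0.95 = 55 evaluable per arm, difference 2.5 − 1.0 = 1.5, SD 2.1, two-sided 5%. This gives 96.0% power per comparison and 90.7% for all three gate-kept comparisons, so 58 per arm (232 in total) reproduces as more than 90% for the whole sequence. It is unaffected by this point and only supplies the 55 per arm used below.

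**Assumptions.** The documents give no correlations. Let r be the outcome's baseline-to-follow-up correlation, a the correlation of baseline MMS with the outcome's baseline, and b that with the outcome at follow-up. Variances at baseline and follow-up are taken as equal and set to 1.

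**Residual variances.**
- Change, given baseline MMS: 2(1 − r) − (b − a)²
- Score, given baseline MMS: 1 − b²
- Either one, given baseline MMS and own baseline: 1 − (r² + b² − 2rab)/(1 − a²)

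Example with r = 0.5, a = −0.3, b = −0.2: change 1 − 0.01 = 0.99; both baselines 1 − (0.25 + 0.04 − 0.06)/0.91 = 0.747; ratio 1.325.

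**IBDQ change: variance without own baseline divided by variance with it.**

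| r | a = b = 0 | a = −0.3, b = −0.2 | a = −0.5, b = −0.3 |
|---|---|---|---|
| 0.3 | 1.538 | 1.550 | 1.545 |
| 0.5 | 1.333 | 1.325 | 1.286 |
| 0.7 | 1.176 | 1.157 | 1.105 |
| 0.8 | 1.111 | 1.089 | 1.038 |

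The inflation is 4% to 55%. In the a = b = 0 column the ratio is 2/(1 + r), and the standard error is 24%, 15%, 8% and 5% larger as r rises. There, 55 patients per arm act like about 36, 41, 47 and 50. A comparison with 90% power when adjusted would have about 74%, 80%, 85% and 87%.

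**IBDQ score.** The pattern runs the other way: the ratio is 1.034 to 1.099 at r = 0.3, 1.219 to 1.333 at 0.5, and 2.625 to 2.778 at 0.8.

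**Daily stool frequency, as a raw value.** Baseline MMS contains the screening stool sub-score, so assume a = 0.6 and b = 0.6r. The ratio is (1 − 0.36r²)/(1 − r²):
- r = 0.3: 0.9676/0.91 = 1.063
- r = 0.5: 0.91/0.75 = 1.213
- r = 0.7: 0.8236/0.51 = 1.615

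The standard error is 3%, 10% and 27% larger, and 90% power becomes about 88%, 84% and 72%.

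**Score against change.** With own baseline as a covariate, the parametric score and change models give the same treatment estimate. Without it, they differ by the MMS-adjusted imbalance in baseline IBDQ. One standard error of that imbalance is √(2/55) × √(1 − a²): 0.191 × 0.954 = 0.18 SD at a = −0.3 and 0.191 × 0.866 = 0.17 SD at a = −0.5.

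**Adding or replacing.** Take r = 0.8, a = −0.5, b = −0.25. Change given MMS has variance 0.4 − 0.0625 = 0.3375; given own baseline alone, 1 − 0.64 = 0.36. Replacing MMS would raise the variance by about 7% (0.36/0.3375 = 1.067). Using both avoids this.

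**The case against.** **The reference to the primary procedure may be loose.** In SAP 15.1.3, baseline MMS is the analysed outcome's own baseline, so the same procedure for IBDQ could mean baseline IBDQ. The list also sends category frequencies and responder counts to ANCOVA, which suggests it was drafted quickly. SAP 7.1 does not call its list exhaustive and refers to the specific analysis sections, and blacked-out lines after the list in SAP 15.2.3.1 cannot be checked. Still, no readable text makes the substitution. SAP 7.1 names own baselines for exactly the six MMRM outcomes and not for these two, so a programmer following the text would fit baseline MMS.

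**Baseline is partly accounted for.** This stands. IBDQ change subtracts its baseline, MMS includes a stool sub-score, and pMMS, which contains stool frequency, gets its own baseline in SAP 15.2.3.3. A reader might infer that baseline is ignored altogether; that goes too far.

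**Bias.** A reader might infer that regression to the mean biases the contrast. It does not: under randomization it affects all arms equally in expectation. What remains is lost precision and the effect of chance imbalance in the one trial.

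**A conflict with the protocol.** Protocol 9.2 says of its mixed model that "baseline values of the respective measurements will be covariates". A reader might infer that the SAP departs from this for IBDQ and stool frequency. Neither is on that model's list, so there is no conflict. The comparison shows only that own-baseline adjustment is normal practice elsewhere in the plan.

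**Size.** A narrower assumption, r of 0.4 to 0.6 with equal variances, would suggest that replacing MMS by baseline IBDQ cuts residual variance by 13% to 29%, worth 15% to 40% more patients. The documents do not support so firm a figure. If the Week 8 SD is 1.2 times the baseline SD, the cut is 4% to 17%.

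**Conclusion.** The point holds as one of precision and specification. As written, the SAP analyses total IBDQ score, IBDQ change and daily stool frequency with screening MMS as the only continuous covariate, although each outcome's own baseline is collected. Omitting it increased residual variance in every scenario tried, but the size rests on assumed correlations and equal variances. For IBDQ change the loss is modest when r is near 0.8. For raw stool frequency it is small when r is near 0.3. The possible disagreement between the IBDQ score and change models does not depend on r.

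The outcomes are secondary and outside the gate-keeping sequence for the primary endpoint, and the primary MMS analysis is untouched. The change is worth making because it is cheap, not because any result would be invalid without it.

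**What to change.** In SAP 7.1 and 15.2.3.1, state that each continuous outcome's own baseline enters its model: Day 1 total IBDQ for the IBDQ models, and pre-dose e-diary stool frequency for the stool model. Add these to baseline MMS rather than necessarily replacing it.

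Alternatively, move both outcomes to the MMRM of SAP 15.2.3.3, which uses each variable's own baseline. This also helps the Week 16 estimate when Week 16 values are missing. SAP 7.3 and 15.2.2 give missing-data rules for the Mayo components but none for IBDQ. The Week 8 ANCOVA already uses the Week 8 data of patients who leave later, so the MMRM's missing-data benefit described here is for Week 16.

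The cost is a few lines of SAP wording and one extra model term per outcome. No new data are needed.
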